8.3. Efficacy Assessments

While the study will not be powered for efficacy assessments, ILI will be tracked as an exploratory objective in the Phase 1/2, Phase 2 NH, and Phase 2 Extension parts of the study. Active and passive surveillance for influenza will be performed and assessed as part of an exploratory objective in the Phase 2 NH part.

8.4. Safety Definitions and Related Procedures

8.4.1. Adverse Event

An AE is defined as any untoward medical occurrence associated with the use of a drug/vaccine in humans, whether or not considered related to the drug/vaccine.

Events Meeting the Adverse Event Definition

- Exacerbation of a chronic or intermittent pre-existing condition, including an increase in frequency and/or intensity of the condition, after the IP injection.
- New conditions detected or diagnosed after the IP injection even though they may have been present before the start of the study.

Events NOT Meeting the Adverse Event Definition

- Procedures planned before study entry (eg, hospitalization for preplanned surgical procedure).
- Medical or surgical procedure (eg, endoscopy, appendectomy): the condition that leads to the procedure should be the AE.
- Situations in which an untoward medical occurrence did not occur (social and/or convenience admission to a hospital).

An AR is any AE for which there is a reasonable possibility that the vaccine caused the AE ([Section 8.4.3](#)). For the purposes of IND safety reporting, “reasonable possibility” means that there is evidence to suggest a causal relationship between the vaccine and the AE.

An unsolicited AE is any AE reported by the participant that is not specified as a solicited AR in the protocol or is specified as a solicited AR but starts outside the protocol-defined period for reporting solicited ARs (ie, 7 days after vaccine administration).

8.4.2. Serious Adverse Events

An AE (including an AR) is considered an SAE if, in the view of either the Investigator or Sponsor, it results in any of the following outcomes:

- **Death**
A death that occurs during the study or that comes to the attention of the Investigator during the protocol-defined follow-up period must be reported to the Sponsor, whether or not it is considered related to the IP.
- **Is life-threatening**
An AE is considered life-threatening if, in the view of either the Investigator or the Sponsor, its occurrence places the participant at immediate risk of death. It does not include an AE that, had it occurred in a more severe form, might have caused death.
- **Inpatient hospitalization or prolongation of existing hospitalization**
In general, inpatient hospitalization indicates the participant was admitted to the hospital or emergency ward for at least 1 overnight stay for observation and/or

treatment that would not have been appropriate in the physician's office or outpatient setting. The hospital or emergency ward admission should be considered an SAE regardless of whether opinions differ as to the necessity of the admission.

Complications that occur during inpatient hospitalization will be recorded as AEs; however, if a complication/AE prolongs hospitalization or otherwise fulfills SAE criteria, the complication/AE will be recorded as a separate SAE.

- **Persistent or significant incapacity or substantial disruption of the ability to conduct normal life functions**

This definition is not intended to include experiences of relatively minor medical significance such as uncomplicated headache, nausea/vomiting, diarrhea, influenza, and accidental trauma (eg, sprained ankle) that may interfere with or prevent everyday life functions but do not constitute a substantial disruption.

- **Congenital anomaly or birth defect**
- **Medically important event**

Medical judgment should be exercised in deciding whether SAE reporting is appropriate in other situations, such as important medical events that may not be immediately life-threatening or result in death or hospitalization but may jeopardize the participant or require medical or surgical intervention to prevent 1 of the other outcomes listed in the above definition. These events should usually be considered serious. Examples of such medical events include allergic bronchospasm requiring intensive treatment in an emergency room or at home, blood dyscrasias, or convulsions that do not result in inpatient hospitalization, or the development of drug dependency or drug abuse.

8.4.3. Solicited Adverse Reactions

The term “reactogenicity” refers to the occurrence and intensity of selected signs and symptoms (ARs) occurring after the IP injection. The eDiary will solicit daily participant reporting of ARs using a structured checklist ([Section 8.1.1](#)). Participants will record such occurrences in an eDiary on the day of injection and for the 6 days after the day of injection.

Severity grading of reactogenicity will occur automatically based on participant entries into the eDiary according to the grading scales presented in [Table 13](#), which are modified from the toxicity grading scale for healthy adult and adolescent volunteers enrolled in preventive vaccine clinical trials ([DHHS 2007b](#)).

If a participant reported a solicited AR during the solicited period and did not record the event in the eDiary, the event should be recorded on the Reactogenicity page of the eCRF.

If the event starts during the solicited period, but continues beyond 7 days after dosing, the participant should notify the site to provide an end date to close out the event on the Reactogenicity page of the eCRF.

If the participant reported an event after the solicited period (ie, after Day 7), it should be recorded as an AE on the AE page of the eCRF.

All solicited ARs (local and systemic) will be considered causally related to study vaccination.

Table 13 Solicited Adverse Reactions and Grades

Reaction	Grade 1	Grade 2	Grade 3	Grade 4
Injection site pain	Does not interfere with activity	Repeated use of over-the-counter pain reliever > 24 hours or interferes with activity	Any use of prescription pain reliever or prevents daily activity	Requires emergency room visit or hospitalization
Injection site erythema (redness)	25 - 50 mm/ 2.5 - 5 cm	51 - 100 mm/ 5.1 - 10 cm	> 100 mm/ > 10 cm	Necrosis or exfoliative dermatitis
Injection site swelling/induration (hardness)	25 - 50 mm/ 2.5 - 5 cm	51 - 100 mm/ 5.1 - 10 cm	> 100 mm/ > 10 cm	Necrosis
Axillary (underarm) swelling or tenderness ipsilateral to the side of injection	No interference with activity	Repeated use of over-the-counter (nonnarcotic) pain reliever > 24 hours or some interference with activity	Any use of prescription (narcotic) pain reliever or prevents daily activity	Emergency room visit or hospitalization
Headache	No interference with activity	Repeated use of over-the-counter pain reliever > 24 hours or some interference with activity	Significant; any use of prescription pain reliever or prevents daily activity	Requires emergency room visit or hospitalization
Fatigue	No interference with activity	Some interference with activity	Significant; prevents daily activity	Requires emergency room visit or hospitalization

Reaction	Grade 1	Grade 2	Grade 3	Grade 4
Myalgia (muscle aches all over body)	No interference with activity	Some interference with activity	Significant; prevents daily activity	Requires emergency room visit or hospitalization
Arthralgia (joint aches in several joints)	No interference with activity	Some interference with activity	Significant; prevents daily activity	Requires emergency room visit or hospitalization
Nausea/vomiting	No interference with activity or 1 or 2 episodes/24 hours	Some interference with activity or > 2 episodes/24 hours	Prevents daily activity, requires outpatient intravenous hydration	Requires emergency room visit or hospitalization for hypotensive shock
Chills	No interference with activity	Some interference with activity not requiring medical intervention	Prevents daily activity and requires medical intervention	Requires emergency room visit or hospitalization
Fever (oral)	38.0°C - 38.4°C 100.4°F - 101.1°F	38.5°C - 38.9°C 101.2°F - 102.0°F	39.0°C - 40.0°C 102.1°F - 104.0°F	> 40.0°C > 104.0°F

Abbreviations: AE = adverse event; eCRF = electronic case report form,

Note: Events listed above but starting > 7 days post study injection will be recorded on the AE page of the eCRF. Causality for each event will be determined per assessment by the Investigator.

Any solicited AR that meets any of the following criteria must be entered into the participant's source document and must also be recorded by the study site staff in the solicited AR section of the participant's eCRF:

- Solicited local or systemic AR that results in a visit to a healthcare practitioner (HCP), to be recorded as an MAAE ([Section 8.4.4](#)).
- Solicited local or systemic AR leading to the participant withdrawing from the study or the participant being withdrawn from the study by the Investigator (AE leading to withdrawal).
- Solicited local or systemic AR lasting beyond 7 days after injection.
- Solicited local or systemic AR that otherwise meets the definition of an SAE.

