
 To evaluate the safety and reactogenicity of mRNA-1010 vaccine 	
 Frequency and grade of each solicited local and systemic reactogenicity ARs during a 7-day follow-up period after vaccination Frequency and severity of any unsolicited AEs during the 28-day follow-up period after vaccination Frequency of any SAEs, AESIs, and MAAEs from Day 1 through Day 181/EoS
Secondary	

 To evaluate the humoral immunogenicity of each vaccine group against vaccine-matched influenza A and B strains at Day 29 	
 The frequency of participants with HAI seroconversion and the frequency of participants with an HAI titer $\geq 1:40$ at Day 29 GMFR comparing Day 29 to Day 1 (baseline) as measured by HAI
Exploratory (May be Performed)	

 To evaluate the relative vaccine efficacy of mRNA-1010 vaccine to an active comparator in preventing RT-PCR-confirmed ILI caused by any strain of influenza using different case definitions 	
 RT-PCR-confirmed protocol- or CDC-defined ILI that begin at least 14 days after vaccination through Day 181/EoS caused by any strain of influenza regardless of antigenic match to the strains selected for the seasonal vaccine

 To evaluate the humoral immunogenicity of mRNA-1010 vaccine to that of an active comparator against vaccine-matched or vaccine-mismatched influenza A and B strains, including the use of alternative methods 	
 GMT and GMFR of anti-HA antibodies as measured by assays such as MN assays or alternative methods against vaccine-matched or vaccine-mismatched strains on Day 29 compared with Day 1 (baseline) GMT and GMFR of anti-HA antibodies as measured by HAI against vaccine-mismatched strains on Day 29 compared with Day 1 (baseline)

 To evaluate the humoral immunogenicity at Days 91 and 181/EoS in a subset of participants 	
 GMT, GMFR, and frequency of participants with HAI titers $\geq 1:40$ at Days 91 and 181/EoS

 To further characterize the immune response to mRNA-1010 vaccine and active comparator 	
 Frequency, specificities, or other endpoints to be determined for further characterization of immune responses

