- Passive and active surveillance of ILI (Phase 2 NH part only; [Section 8.1.6](#)). Participants will record symptoms of ILI that they may experience anytime from Day 1 through Day 181/EoS as part of the passive ILI surveillance. For active ILI surveillance, participants will be instructed to report whether ILI symptoms have been experienced, 3 to 4 times weekly from Day 1 through Day 29 and twice weekly from Day 30 through Day 181/EoS, via eDiary or telephone calls. If symptoms occur, participants will be directed to return to the study site as soon as possible, but no later than 72 hours after the onset of symptoms, for medical evaluation and an NP swab. Participants will be contacted by the study site, if they have missed reporting in the eDiary. If there is no response to an eDiary prompt for 2 consecutive entries, the study site staff will contact the participant by telephone ([Section 8.1.6](#)).
- Daily oral body temperature measurement should be performed at approximately the same time each day using the thermometer provided by the study site. If body temperature is taken more than once in a given day, only the highest temperature reading should be recorded.

- Measurements, as applicable, for solicited local ARs (injection site erythema and swelling/induration) will be performed using the ruler provided by the study site.
- Any medications taken to treat or prevent pain or fever on the day of injection or for the next 6 days.

The eDiary will be the only source document allowed for solicited systemic or local ARs (including body temperature measurements). Participants will be instructed to complete eDiary entries daily. Quantitative temperature recordings and measurement of any injection site erythema or swelling/induration reported on the following day may be excluded from the analyses of solicited ARs.

Study site staff will review eDiary data with participants at a visit 7 days after the injection.

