6.3.2 Solicited Adverse Reactions

An AR is any AE for which there is a reasonable possibility that the IP caused the AE. The term “Solicited Adverse Reactions” refers to selected signs and symptoms occurring after injection administration during a specified post-injection follow-up period (day of injection and 6 subsequent days). The solicited ARs are recorded by the participant in the eDiary.

Any new safety information reported during safety telephone calls or at site visits (including a solicited reaction) that is not already captured in the eDiary will be described in the source documents as a verbally reported event. Any AR reported in this manner must be entered on the Reactogenicity eCRF and will be included in the evaluation of solicited ARs in addition to the eDiary data.

The occurrence and intensity of selected signs and symptoms are actively solicited from participants during a specified post-injection follow-up period (day of injection and 6 subsequent days), using a pre-defined checklist (i.e., solicited ARs). If a solicited local or systemic AR continues beyond 7 days post injection, the participant will be prompted daily to capture solicited local or systemic AR in the eDiary until no longer reported, not to exceed 28 days after vaccination.

The following local ARs will be solicited: injection site pain, injection site erythema (redness), injection site swelling/induration (hardness), and axillary (underarm) swelling or tenderness ipsilateral to the side of injection.

The following systemic ARs will be solicited: fever (an oral temperature greater than or equal to 38.0°C/100.4°F), headache, fatigue, myalgia (muscle aches all over the body), arthralgia (joint aches in several joints), nausea/vomiting, and chills.

The solicited ARs will be graded based on the grading scales presented in the protocol, modified from the Toxicity Grading Scale for Healthy Adult and Adolescent Volunteers Enrolled in Preventative Vaccine Clinical Trials (DHHS 2007). The investigator will assess Grade 4 (with exception of fever) solicited ARs recorded in eDiary or Reactogenicity CRF.

Analyses of solicited ARs will be provided by vaccination group (and then by age group) based on the Solicited Safety Set, unless otherwise specified. All solicited ARs (overall, local, and systemic) reported during the 7-day follow-up period after injection will be summarized. All solicited ARs will be considered causally related to injection.

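### Protocol 8.4.3 picks the eCRF page for a listed reaction by when it was reported, while 8.4.1, the Table 13 note and SAP 6.3.2 do not, so some Day 1-7 reactions may be missed by the solicited AR summaries

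*Protocol*

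**What the plan says.** Protocol 8.4.3 has three consecutive instructions on where a listed reaction is recorded.

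- The first covers reactions missing from the diary: "If a participant reported a solicited AR during the solicited period and did not record the event in the eDiary", in which case the Reactogenicity page is used.
- The second covers a reaction that starts in the period and runs past it. It is closed out on the Reactogenicity page.
- The third is: "If the participant reported an event after the solicited period (ie, after Day 7), it should be recorded as an AE", on the AE page.

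The first and third depend on when the participant spoke. The second depends on when the event began.

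Two other protocol statements use onset. The unsolicited AE definition in 8.4.1 takes in a listed reaction only if it "is specified as a solicited AR but starts outside the protocol-defined period for reporting solicited ARs". The note under Table 13, also in 8.4.3, reads: "Events listed above but starting > 7 days post study injection will be recorded on the AE page of the eCRF".

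SAP 6.3.2 deals with reactions that come up at a call or visit and are not in the eDiary: "Any AR reported in this manner must be entered on the Reactogenicity eCRF". It then counts them with the diary data as solicited ARs and sets no deadline for the report.

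Protocol 8.1.1 adds a further statement: "The eDiary will be the only source document allowed for solicited systemic or local ARs". It also sets the routine review: "Study site staff will review eDiary data with participants at a visit 7 days after the injection".

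**The concern.** The routine staff review falls just after the solicited period ends. Diary entries run over Days 1-7 and the review is nominally on Day 8. A participant who skipped the diary and mentions an early reaction at that review is reporting after Day 7. The third sentence of 8.4.3 then points to the AE page, although the reaction began well inside the solicited period. Had the same contact taken place a day or two earlier, still within its window, the first sentence would have pointed to the Reactogenicity page.

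Both destinations feed primary endpoints. One is "Frequency and grade of each solicited local and systemic reactogenicity ARs during a 7-day follow-up period after vaccination". The other is unsolicited AEs over 28 days. A misplaced record lowers the first and can raise the second. It also arrives under different conventions. Table 13 grades are replaced by the Investigator's mild, moderate or severe rating (8.4.10). Causality is assessed by the Investigator (8.4.11), whereas 8.4.3 treats all solicited ARs as related.

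**Working it through.** The plan states no figure on this point, so the check compares the rules, then the timing, then the weight of one record.

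**1. The rules applied to the same events**

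| Event | 8.4.3 sentences on reporting | Other protocol text | SAP 6.3.2 |
|---|---|---|---|
| A. Onset Day 3, not in eDiary, resolved, no healthcare visit, first told Day 8 | AE page | Not an unsolicited AE (8.4.1); not sent to the AE page by the Table 13 note | Reactogenicity eCRF |
| B. As A, first told Day 6 | Reactogenicity page | Same as A | Reactogenicity eCRF |
| C. As A, but still ongoing after Day 7 | AE page if the third sentence is read alone | Reactogenicity page (second sentence of 8.4.3) and solicited AR section (list after Table 13) | Reactogenicity eCRF |
| D. As A, but led to a healthcare visit or withdrawal, or was serious | AE page if the third sentence is read alone | Solicited AR section (list after Table 13) | Reactogenicity eCRF |
| E. Onset Day 20, told Day 29 | AE page | AE page (8.4.1, Table 13 note) | Outside the SAP's 7-day definition of a solicited AR |

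Event A is the unresolved conflict. For C and D, explicit text in 8.4.3 keeps the reaction in the solicited section. For B and E the sources agree.

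**2. Timing of the Day 8 contact (schedules of events)**

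- Phase 1/2: Day 8, -2 or +1, gives Days 6-9. Days 8-9 fall after Day 7, which is 2 of 4 permitted days.
- Phase 2 NH and Extension: Day 8 ±3 gives Days 5-11. Days 8-11 fall after Day 7, which is 4 of 7 permitted days.

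The target day is affected in every part. These counts are of permitted days, not of how often contacts fall on them.

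**3. Whether the analysis would recover the record**

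SAP 6.3.2 builds its by-day solicited AR summaries, and its maximum-grade listing, from the eDiary and the Reactogenicity CRF. No SAP rule looks for listed terms with Day 1-7 onset on the AE page. SAP section 7 declares no departure from the protocol.

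**4. Weight of one record**

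Shift in a solicited AR percentage per affected participant = 100 / n, at the planned group sizes:

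- Phase 1/2 groups, n=45: 100/45 = 2.2 points.
- Extension groups and the NH comparator, n=50: 100/50 = 2.0 points.
- NH mRNA-1010 groups, n=150: 100/150 = 0.67 points.

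The participant is assumed to stay in the denominator. That is reasonable, because 8.1.1 has a supervised diary entry made about 1 hour after injection, which is enough to enter the Solicited Safety Set. The shift occurs only if that reaction appears on none of the participant's Day 1-7 diary entries. For the any-reaction rate, it occurs only if no other solicited reaction was captured.

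**The case against.** The strongest reply is that the documents already give the right answer. SAP 6.3.2 counts verbally reported solicited reactions as solicited, and SAP section 1 says the SAP prevails where methods differ. Under 8.4.1 a Day 3 reaction is not an unsolicited AE, whichever page holds it. This defeats the inference, which a reader might draw, that such reactions necessarily leave the reactogenicity endpoint and become unsolicited AEs. It does not remove the risk. The precedence clause covers analysis methods, while sites complete the eCRF from the protocol, and the SAP has no step to retrieve a record already on the AE page.

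A reader might also infer that every early reaction told verbally after Day 7 is misplaced. The text does not support that. 8.4.3 keeps in the solicited section reactions that last beyond 7 days, lead to a healthcare visit or withdrawal, or are serious, with no condition on report date.

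Nor does the SAP's missing reporting deadline mean that it lacks an onset limit. It defines solicited ARs as occurring on the day of injection and the 6 days after, so a late-onset headache would not qualify.

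Earlier contact is possible. The Extension has an optional Day 4 visit, and 8.4.9 has staff ask about well-being at every visit or call. In NH, two unanswered ILI diary prompts trigger a telephone call. These reduce the number of late first reports but do not settle where one is recorded.

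Finally, no hypotheses are tested, and the contact schedule is the same for all groups within a part. The effect would be on descriptive rates, not on a test decision. That limits the importance of the point.

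**Conclusion.** The point holds as an internal inconsistency that creates a risk of misclassification. Two sentences of Protocol 8.4.3 choose the page by report date, against an onset rule in 8.4.1 and the Table 13 note and against SAP 6.3.2. Exposure is confined to resolved, non-serious, non-attended reactions with onset on Days 1-7 that are absent from the eDiary, did not lead to withdrawal, and are first reported on Day 8 or later.

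The documents give no frequency for such reports, so no overall bias can be stated. What can be stated is 0.67, 2.0 or 2.2 percentage points per affected participant at n=150, 50 or 45. This assumes that the site follows the 8.4.3 sentence literally and that the record is not re-entered on the Reactogenicity page. It should be corrected because it touches a primary endpoint and the remedy is small. It does not show that the solicited AR results will be wrong.

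**What to change.** 1. In Protocol 8.4.3, replace the report-date sentences with one onset rule. A listed reaction with onset on Days 1-7 goes on the Reactogenicity page whenever it is reported, and one with onset after Day 7 goes on the AE page. State it in study days: Day 8 is exactly 7 days after injection, so the Table 13 wording of more than 7 days leaves that day unclear.
2. Reconcile the sole-source statement in 8.1.1 with the Reactogenicity-page rule, which depends on reports made outside the eDiary.
3. In SAP 6.3.2, state that solicited ARs are classified by onset date, and that AE-page records of listed terms with onset on Days 1-7 are included in the solicited AR tables. To avoid double counting, they should then be left out of the unsolicited tables.

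The cost is a few sentences across the protocol, the eCRF completion guidance and the SAP, plus one programmed derivation before database lock. Onset is already collected for AE-page events (8.4.12), so no new data are needed, and the derivation also covers records already entered.
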